One hundred and fifty treatment seeking alcohol dependent individuals (men and women) will be recruited to participate in this medication study. Subjects may or may not participate in laboratory sessions. Subjects will be recruited through flyers and advertisements in local newspapers and from community substance abuse treatment facilities. Subjects will participate in an initial screening and intake session to obtain informed consent, followed by physical examination and blood work to determine eligibility. Subjects will be randomized to Prazosin (PRZ) or placebo (PLA) and medication will be dispensed in a three times daily dosing schedule (t.i.d. dosing) with 5 mg in the morning, 5 mg in the afternoon and 6 mg at night reached at the end of the 2-week period, and maintained at this or their highest tolerated dose until week 11, followed by a 5-day taper in week 12, as in previous research. The titration schedule was as follows: 1 mg dose at bedtime for 2 nights, followed by a 1mg dose morning and night (8 AM/8 PM) on day 3, then 2 mg dose t.i.d., on days 4-6, 3 mg dose (2 pills each) morning and afternoon, and 4 mg dose (2 pills) at night for days 7-9, increased to 4 mg dosing t.i.d. on days 10-13, and from day 14 through week 11, 5 mg (1 pill) each in the morning and afternoon, and 6 mg for the night (2 pills) dose. Subjects will be maintained on this dose during the laboratory sessions (if completing the laboratory sessions) and until week 12 of the study at which point they will be tapered off the study medication over the course of five days. Some subjects may be tapered prior to completion of the 12 weeks. This taper is similar to what has been used with lofexidine in opiate withdrawal protocols (Bearn et al., 1996; Strang et al., 1997) and in our outpatient relapse prevention study of lofexidine with opiate dependent patients. We expect most subjects will tolerate a daily dose of 16.0mg. However, subjects who cannot tolerate a dosing schedule of 16.0 mg will meet with the study psychiatrist to discuss a reduction in dose down to 10mg/day. Based on the Physician Desk Reference (2007), which reports that dosage may be as high as 40mg daily, we anticipate that 16.0mg per day will be well tolerated by subjects. Subjects who cannot tolerate a minimum dose of 6mg/day will be removed from the study protocol.

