After a subject is able to abstain from substances for a period of 21+ days, they will have the option to complete a 3-night stay on the CNRU, where they will participate in imagery training and 3 laboratory sessions. After completion of the laboratory sessions, subjects will be discharged from the inpatient unit at least one day after the laboratory sessions.

Subjects will undergo the same titration onto study medication as outlined above. If the subject decides to complete the laboratory component, they will be maintained on 16.0mg dose of PRZ/PLA medication during the week of the inpatient laboratory sessions, after which they will undergo the above mentioned taper or continue to take their medication for 9 weeks in outpatient

treatment. In the event that someone continues to use alcohol while in the study, they may be asked to come in for more frequent appointments to assess for adverse symptomatology and meet with the study psychiatrist. Similar methods have been used in our outpatient lofexidine study and no adverse interaction events are anticipated.

Table 1: PRZ/PLA Dosing

	Prazosin PRZ (N = 75) (Male / Female)			Placebo (PLA) (N = 75) (Male / Female)		
Week 1	AM	PM	Evening	AM	PM	Evening
Days 1 -2 (1mg / 1mg)	0mg / 0mg	0mg / 0mg	1mg / 1mg	0mg / 0mg	0mg / 0mg	1mg / 1mg
Days 3 (2mg /1mg)	1mg / 0mg	0mg / 0mg	1mg / 1mg	1mg / 0mg	0mg / 0mg	1mg / 1mg
Days 4-6 (6 mg/4mg)	2mg/1mg	2mg/1 mg	2 mg/2mg	2mg/1mg	2mg/1 mg	2mg/2mg
Week 2						
Days 7-9 (10mg /8mg)	3mg / 2mg	3mg / 2mg	4mg /4mg	3mg / 2mg	3mg / 2mg	4mg /4mg
Days 10 – 13 (12mg/12mg)	4mg /4mg	4mg/4mg	4mg /4mg	4mg /4mg	4mg /4mg	4mg /4mg
Day 14 (16mg/16mg)	5mg/5mg	5mg/5mg	6mg/6mg	5mg/5mg	5mg/5mg	6mg/6mg

Follow-up:

Upon completion of outpatient treatment, follow-up interviews will be scheduled with all subjects. If a subject decides to complete only the inpatient phase, follow-up appointments will be scheduled after the inpatient phase is complete. Follow up interviews will be scheduled at 30 days. Urine monitoring, assessment of craving, cocaine abstinence symptoms, self report of drug use and stress and craving scales, will be assessed during the follow-up appointment.

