Contact and collateral information will have been obtained from subjects at intake. We currently use procedures that make it possible to locate and re-interview more than 90% of the patients recruited into our treatment and laboratory research studies. Of note, in our recently completed stress study with cocaine dependent individuals we obtained a 92% completion rate. Our procedures include informing the patient of the importance of follow-up evaluations at the time of initial assessment, emphasizing the patient's role as a research subject, guaranteeing complete confidentiality of all information, obtaining permission, addresses and telephone numbers of three collaterals to be contacted in order to help us locate the subject, arranging for home visits and telephone interviews when subjects fail to keep appointments, mailing of appointment reminders that are followed by telephone calls, and provision of incentive payments for successful completion of follow-up evaluations. All of these procedures will be incorporated into this study.

Study Feasibility:

The Chronic Alcohol and Brain Stress Circuit Relapse (#22015) for alcohol addiction currently screens approximately 15 subjects per month. On average, approximately 6-8 patients meet criteria for the proposed study (not on other medications and otherwise healthy) and will be offered participation in this study. Thus we anticipate that 3-4 patients can be enrolled into the pilot study monthly, leading to a 15-20 month recruitment phase for this study. The subjects will be recruited from treatment seeking individuals who are being evaluated for alcohol treatment at clinical programs and from those responding to advertisements and flyers for inpatient treatment and research.

General Procedures:

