All subjects will also be seen two times per week in outpatient treatment at the Yale Stress Center. All subjects will participate in 1x per week standard individual drug counseling as outlined in the Individual Drug Counseling Manual (IDC, Mercer & Woody, 1998) during the outpatient trial. Each subject will be assigned a counselor with expertise in IDC. The general purpose of the counseling sessions as described in the manual are to: (1) acquire information about important concepts and aspects of recovery from addiction; (2) increase self-awareness of specific problems and issues in relation to addiction and recovery, and (3) learn new coping skills to deal with problems contributing to or resulting from the addiction and to improve functioning. The focus of this psycho-educational approach is on providing patients with frequent supportive contact, introduce them to key concepts about the recovery approach, and develop a sense of personal responsibility for recovery.

Relapse in the pilot study will be defined as the first day of any alcohol use as documented by self-report and/or positive urine and positive breathalyzer for alcohol. Treatment drop-out is defined as four consecutive missed research appointments for medication self-administration. Relapse to alcohol will be recorded in the data and subjects will continue in the protocol. Furthermore, it will be addressed by their counselor and doctor in therapy appointments. If subjects have missed four consecutive appointments, all attempts will be made to bring the subject back and after a full assessment of the subject's need, a formal referral will be made to appropriate residential, inpatient or intensive outpatient care. Subjects will be maintained in regular treatment until they have entered treatment at the next appropriate level of care. Other clinical deterioration such as exacerbation of psychiatric or withdrawal symptoms will be assessed on a case-by-case basis by the study investigators. When clinically indicated and necessary, psychotropic medication or discontinuation of study medication will be initiated and/or a referral will be made to intensive outpatient, residential or inpatient care.

Physiological Assessments

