The Structured Clinical Interview for DSM-IVTR (SCID, First et al., 1995) will be used to obtain DSM-IVTR Alcohol Dependence and other substance use disorder diagnoses. The SCID's reliability and validity among substance-using populations has been established in large-scale surveys (Kranzler et al., 1996). The number of dependence syndrome elements endorsed from the DSM-IVTR substance abuse/dependence criteria will assess severity of alcohol and other drug dependence. The SCID will also be used to obtain previous psychiatric diagnoses.

Medical History and Physical Examination: All patients will be required to participate in a physical examination including a medical history, electrocardiogram (EKG), blood and urine laboratory assessments prior to initiation of Prazosin to ensure eligibility for Prazosin study protocol. These will be conducted at the CNRU.

Short Form 36 Health Survey (SF-36) is a 36-Item questionnaire used in to assess the subjective quality of life of respondents.

Drug and Alcohol Use Measures:

Addiction Severity Index (ASI: McLellan et al., 1992) is a structured interview that assesses the severity of substance use and substance-related problems in the areas of medical, employment, legal, family/social and psychiatric functioning. The ASI is the most widely used instrument for assessment of substance use and related problems and its psychometric properties are well-established (Cacciola et al., 1997). The ASI will be used at pre-treatment and week 9. Follow-up ASI interviews will be conducted at 30 days post-treatment.

The Substance Use Calendar was developed by Miller and DelBoca (1994) and is based on the Time-Line Follow-Back Method (TLFB) (Sobell, Maisto et al. 1980). The SUC uses a calendar prompt and a number of other memory aids (e.g., holiday, payday, and other personally relevant dates) to facilitate accurate recall of daily drug use during the targeted period. It has demonstrated adequate levels of reliability and validity when administered as an in-person interview, over the telephone, and when administered via computer (e.g. Carey, 1997; Sobell, Brown, Leo, & Sobell, 1996; Sobell, Sobell, Leo & Cancilla, 1988). It's reliability and validity in drug abusing samples has also been established (Fals-Stewart, et al., 2000). In the current study we will use to obtain self-report of day to day use of alcohol and drugs, for the 60 days prior to treatment, weekly during treatment, and at the 30 day follow-up interviews.

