Data Analytic Procedures: Since patients will be randomly assigned to the Prazosin and PLA treatment groups and Intent-to-Treat (ITT) analyses will be conducted for the clinical outcomes. We do not expect the groups to be different on demographic, prior drug use history or other predictor variables. Nevertheless, prior to undertaking the specific analysis for each aim, we will compare the treatment groups on demographic variables, substance use characteristics and previous psychiatric history/predictor variables using t-tests/chi-square analyses as appropriate. If any group differences are found, the specific variable will be entered as a covariate in all of the specific analyses. As there are no established thresholds for AW effects on drinking outcomes in outpatient treatment, baseline AW will be assessed as continuous measure in all overall analyses. Thus, intent-to-treat (ITT) analyses with baseline AW severity (mean-centered continuous CIWA-Ar scores) as a moderator of Time (Pre-Full Dose(FD): weeks 1-2; Post FD: weeks 3-12) were conducted with linear or generalized linear mixed effect (LME/GLME) piecewise growth models for continuous and binary outcomes. Due to a positive skew, number of drinks per day

(AvgD) will be log-transformed. Control variables in all analyses will be gender (0=male), inpatient (0=outpatient), and dropout (0=completer, 1=dropout/withdrawn prior to 4 weeks, 2=dropout/withdrawn after 4 weeks). For secondary outcomes linear mixed models with random intercepts will be used to assess the effect of AW, Treatment and Week (factor 1-12, or Weeks 4, 8 and 12) on the secondary outcome variables. All control variables from the main outcome analyses are included in the secondary outcome analyses. If significant interactions with AW are observed for primary or secondary outcome analyses, a median split of AW scores will be conducted to obtain Low and High AW groups and assess contrasts by treatment.

Aims and Hypotheses for Laboratory and Treatment Outcome Components: All analyses of the laboratory and the treatment components will be based on the following specific aims and hypotheses:

Specific Aim 1: To evaluate the effects of Prazosin on stress-induced alcohol craving and associated neuroadaptations in alcohol dependent individuals. Hypothesis 1: Prazosin will decrease stress-induced alcohol craving and negative emotions in the laboratory as compared to placebo.

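### Patients who cannot tolerate 6 mg/day leave the study, and the plan assigns no collection of their drinking data from removal to week 12

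*Combined protocol and SAP*

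**What the plan says.** **Removal.** Section V.3 (Research Plan) lets a patient who does not tolerate 16 mg/day step down, and then sets a floor: "Subjects who cannot tolerate a minimum dose of 6mg/day will be removed from the study protocol". Section VI.A.3 (Source) also keeps patients on the dose they can tolerate, but mentions no floor.

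**Collection of drinking data.** Under Drug and Alcohol Use Measures, the Substance Use Calendar is taken "for the 60 days prior to treatment, weekly during treatment, and at the 30 day follow-up interviews". The daily telephone or smartphone survey is described as part of outpatient treatment (Section V.3, Outpatient Plan; Section VI.A.3).

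**Follow-up.** "Upon completion of outpatient treatment, follow-up interviews will be scheduled with all subjects"; a patient who does only the inpatient phase is interviewed after that phase. The interview is set at 30 days. Tracing measures include "arranging for home visits and telephone interviews when subjects fail to keep appointments". General Procedures adds: "If subjects have missed four consecutive appointments, all attempts will be made to bring the subject back".

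**Analysis.** Section V.12 (Data Analytic Procedures) states that "Intent-to-Treat (ITT) analyses will be conducted for the clinical outcomes". The piecewise model splits time as "Pre-Full Dose(FD): weeks 1-2; Post FD: weeks 3-12". Its control variables include a three-level dropout term: completer, left before 4 weeks, left after 4 weeks.

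**The concern.** The removal rule is triggered after randomisation by poor tolerability, and it is worded as leaving the protocol rather than as stopping the drug. The plan makes that distinction elsewhere. General Procedures treats discontinuing study medication as a separate step and keeps relapsing patients in the protocol.

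If the rule is followed as written, primary-outcome data can stop because of a tolerability event, while the analysis is meant to cover everyone randomised through week 12. Data collected before removal stay in the model. Drinking after removal may be missing for a reason connected with treatment. The model then has to assume that, given treatment, covariates and earlier drinking, removed patients went on drinking like comparable patients who stayed. The plan assigns no data collection that would test this.

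**Working it through.** The plan gives no figure on this point to reproduce. The check has two parts: whether any provision covers the interval from removal to week 12, and how many outcome days are exposed.

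**1. Provisions that might cover the interval**

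| Provision | Reaches a removed patient up to week 12? |
|---|---|
| Substance Use Calendar, weekly | Tied to being in treatment; not assigned after removal |
| Daily survey | Tied to outpatient treatment; not assigned after removal |
| 30-day interview, all subjects | Possibly. It is scheduled from completion of outpatient treatment or of the inpatient phase; timing and look-back after removal are not stated |
| Tracing and the four-missed-appointments rule | Acts on missed appointments. It could support the 30-day interview, which is itself an appointment, but creates no weekly contact after removal |
| Dropout term in the model | Adjusts for having left; supplies no outcome data |

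Only the 30-day interview could fill the interval, and what it recovers depends on two details that the plan does not give.

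**2. Full-dose days lost per removed patient**

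Inputs: the full-dose segment is weeks 3-12 (Section V.12), so days 15-84, or 84 - 14 = 70 days. Week 12 ends on day 84, and 30 days later is day 114. Look-back lengths are assumptions; the 60-day figure in the protocol applies to the pre-treatment calendar only.

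| Removal | Interview | Look-back (assumed) | Full-dose days lost |
|---|---|---|---|
| By day 14 | Day 114 | 30 days (covers 85-114) | 70 |
| By day 14 | Day 114 | 60 days (covers 55-114) | 70 - 30 = 40 |
| By day 14 | Day 114 | To last contact | 0 |
| Day 9 | Day 39 | To removal | 84 - 39 = 45 |
| Day 28 | Day 114 | 30 days | 84 - 28 = 56 |
| Day 28 | Day 58 | To removal | 84 - 58 = 26 |
| Day 56 | Day 86 | To removal | 0 |

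The range is therefore 0 to 70 of 70 days. Early removal is plausible. In the PRZ/PLA dosing table men reach 6 mg/day on day 4 and women pass it on day 7, and Section VI.A.2 says side effects tend to come at the lower starting doses. Later removal is also possible, when a patient steps down from a higher dose and then fails 6 mg.

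**3. Loss per arm**

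With 75 patients per arm (dosing table), full-dose patient-days are 75 x 70 = 5,250. No removal rate is given. Assuming 0 to 3 removals before day 15 with nothing recovered:

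- 1 patient: 70 / 5,250 = 1.3%
- 3 patients: 210 / 5,250 = 4.0%

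The loss scales directly with the removal share: under the same worst case, 10% removed would mean 10% of full-dose days. So 210 days is the result of an assumption and not an upper limit.

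A bias figure would need both the removal share in each arm and the difference in drinking between removed and retained patients. The documents give neither.

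**The case against.** **The interview may recover the data.** It is planned for all subjects, the calendar is a retrospective day-by-day method, and the tracing steps are thorough. This stands. If the interview reaches back to last contact, nothing is lost. It narrows the gap to unstated timing and look-back, but does not close it.

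**The wording may not mean full exit.** Section VI.A.3 keeps patients on whatever dose they tolerate and sets no floor; if it governs, nobody leaves at 6 mg/day. But only Section V.3 mentions the 6 mg/day case, and it says removal. Two readings are themselves a reason to settle the text.

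**The model already handles withdrawal.** The dropout term does separate patients who leave before or after 4 weeks, so the plan anticipates them. Yet it is listed as a control variable, with no stated interaction with time. For a patient removed by day 14 with nothing recovered later, every observed day lies in weeks 1-2, so the term cannot show how that patient drank in weeks 3-12.

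**Few patients, and larger exits exist.** Good tolerability is expected, and Section VI.A.2 reports that lowering the dose eased side effects, so numbers are probably small. Section V.9 has other exits, linked to drinking itself, which this point does not address.

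**Stronger readings to resist.** A reader might infer that all drinking data after removal will be lost, that removed patients drop out of the intention-to-treat analysis, or that the result is biased towards prazosin. The documents support none of these. The interview may recover the days, pre-removal data remain, and higher removal on prazosin is only an inference: Section VI.A.2 also reports dizziness on placebo.

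**Conclusion.** The gap holds in a limited form. The plan removes patients who cannot tolerate 6 mg/day and assigns no drinking-data collection from removal to week 12, which works against its own intention-to-treat analysis of weeks 3-12. The exposure is 0 to 70 full-dose days per removed patient. It is 0-4% of an arm's full-dose patient-days if 0 to 3 of 75 are removed before day 15 and nothing is recovered. That count is assumed. No bias size or direction is claimed. The point should be fixed because the remedy is simple and cheap, not because harm to the primary result has been shown. Confidence is medium, since the Section V.3 wording could be read less strictly.

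**What to change.** In Section V.3 (Research Plan), and in matching terms in Section VI.A.3 (Source), state:

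- A patient who cannot tolerate 6 mg/day stops study drug but stays in the study.
- The Substance Use Calendar continues through week 12, by telephone if needed. The protocol already describes it as reliable and valid "when administered as an in-person interview, over the telephone, and when administered via computer".
- The daily survey is optional for these patients, with its medication prompt removed, because the present survey reminds patients to take study drug.
- These data enter the intention-to-treat analysis in Section V.12, and a patient who is off drug but still reporting is not coded as a dropout.

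**Cost.** Up to about 12 calendar contacts of staff time per affected patient; the documents give no price for this. If the survey is kept, payments follow the $20 weekly rate in Section X.2. Removal on day 4 leaves days 5-84, which is 80 days or 80 / 7 = 11.4 weeks, so $20 x 11 to $20 x 12 = $220-240 per patient, or $660-720 for three. No extra drug exposure is involved.

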Subjects will complete a variety of diagnostic, cognitive and psychological assessments, a comprehensive physical examination and blood work. If completing the laboratory component as inpatients, subjects will also be involved in development of imagery scripts from personal stress, drug-related cue and neutral situations during the first 3 weeks of their stay. After subjects have been substance- free for 21+ days, they will participate in an imagery/relaxation training and

habituation session. Between weeks 3 – 4, subjects will participate in a 3-day experiment in which during a 2-hour laboratory session on three consecutive days, subjects will be exposed by guided imagery to a personal stressful situation, a drug cue related situation and a neutral relaxing situation, one exposure per day. Order of imagery type will be randomly assigned across subjects.

Research Plan:

Subjects will have the option of participating in either the inpatient–outpatient plan, or the outpatient plan. The inpatient–outpatient plan involves 3 - 4 weeks of inpatient treatment followed by 8 - 9 weeks of outpatient treatment. Subjects completing the inpatient-outpatient plan may or may not complete the laboratory sessions. The outpatient plan involves outpatient treatment with 12-Step Counseling for 12 weeks. Subjects enrolled in the outpatient plan also have the option to complete 4 days of inpatient laboratory sessions. The provision of an outpatient alternative is added to provide an opportunity for participation to those subjects who are not able to participate in longer inpatient treatment due to childcare, employment, or other related obligations. The three alternatives are described below:

Inpatient-Outpatient Plan with laboratory sessions:

Once a subject is deemed eligible, those who are interested in the inpatient option will be admitted to the Clinical Neuroscience Research Unit (CNRU) of the Connecticut Mental Health Center (CMHC) for the 3 - 4 week stay that will involve medication initiation and laboratory sessions where subjects will be exposed to stress, drug cues and neutral-relaxing cues on three separate consecutive days. Lab sessions will take place either on the Clinical Neuroscience Research Unit (CNRU) or at the Yale Stress Center.

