After completing the inpatient phase of the study, subjects will either taper off the study medication or participate in a 9-week outpatient medication trial. Those choosing to continue treatment will be seen 2 times per week in outpatient treatment at the Substance Abuse Center at CMHC, or at the Yale Stress Center at [name]. Subjects will be maintained on 16.0mg dose of PRZ/PLA until week 12. In week 12, subjects will undergo a 5-day taper similar to what has been used with Lofexidine in opiate withdrawal protocols (Bearn et al., 1996; Strange et al., 1997) and in our outpatient relapse prevention study of Lofexidine and Guanfacine with opiate and cocaine dependent patients respectively. Urine monitoring, assessment of craving, alcohol abstinence symptoms, self report of drug use and stress and craving scales, heart rate and blood pressure will be assessed weekly in the trial.

Inpatient-Outpatient Plan without laboratory sessions:

The plan for subjects completing the Inpatient-Outpatient Plan without laboratory sessions, will be identical to the plan for the Inpatient-Outpatient Plan with laboratory sessions, minus the laboratory sessions, and all procedures related to the laboratory sessions, such as participating in imagery script development sessions. Once a subject is deemed eligible, those who are interested in the inpatient option will be admitted to the Clinical Neuroscience Research Unit (CNRU) of

the Connecticut Mental Health Center (CMHC) for the 3 - 4 week stay that will involve medication initiation.

After completing the inpatient phase of the study, subjects will either taper off the study medication or participate in a 9-week outpatient medication trial. Those choosing to continue treatment will be seen 2 times per week in outpatient treatment at the Substance Abuse Center at CMHC, or at the Yale Stress Center at [name]. Subjects will be maintained on 16.0mg dose of PRZ/PLA until week 12.

Outpatient Plan:

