with medication and alcohol withdrawal/anxiety, we used a conservative effect size of $d = .60$ for detection of significant main effects and possible interactions in the clinical trial. At this effect size and power = .80, with $p < .05$, sample size estimates from Cohen (1988, p.258) indicated that we would require 25 subjects per cell to adequately assess the proposed hypotheses for the clinical trial (total $N = 100$). Including a 15-20% drop-out after enrollment, we estimated recruitment of 120 AD patients into the trial to ensure adequate power for the trial.

Data Analysis for Laboratory Study: Repeated measures ANOVA and mixed model procedures to assess treatment group differences in alcohol craving and stress related changes (heart rate, blood pressure, HPA and catecholamine responses) during laboratory exposure to stress and drug cues as compared to neutral imagery conditions. Non-parametric tests will be used to assess occurrence of side effects, treatment retention rates, alcohol use measures, CIWA scores and perceived stress scores during the outpatient treatment phase. The number and type of AE's for the two treatment groups will be conducted using t-tests, chi-square tests and ANOVAs as appropriate. Findings will be used to estimate effect sizes for the medication and guide the larger randomized clinical trial.

Data Analysis for the 12-week clinical trial Study: For this phase, the following moderator and primary and secondary outcomes are specified:

Primary Moderator Measure: Alcohol withdrawal symptoms, as measured by the CIWA alcohol withdrawal scale,

Primary Outcome Measures in the outpatient treatment phase: These are: (1) Heavy drinking days (5 or more for men, 4 or more for women) during the 12 week period, and (2) Any drinking days. Both will be assessed daily using smartphone or interactive voice recording surveys completed by the patients and also with weekly urine drug screens/breathalyzer reports and self report of drug use on the Substance Use Calendar.

Secondary Outcome Measures in the outpatient treatment phase: Secondary outcome measures will include alcohol craving scales, anxiety (Hamilton Anxiety Scale) and depression (CES-D) and sleep quality using the Pittsburgh Sleep Quality Index – PSQI).

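### Randomised subjects who stop after the inpatient phase are last assessed at about week 7 to 9, so the final 19 to 33 days of the 84-day primary drinking window go unmeasured

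*Combined protocol and SAP*

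**What the plan says.** Section V.3 (Research Plan) describes the combined plan as "3 - 4 weeks of inpatient treatment followed by 8 - 9 weeks of outpatient treatment". Medication starts on the ward. At discharge, "After completing the inpatient phase of the study, subjects will either taper off the study medication or participate in a 9-week outpatient medication trial"; the sentence appears in the plans with and without laboratory sessions. Twice-weekly visits are then described only for those who continue.

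The Follow-up paragraph of the same section says: "If a subject decides to complete only the inpatient phase, follow-up appointments will be scheduled after the inpatient phase is complete". It adds: "Follow up interviews will be scheduled at 30 days". Among the content of that visit, "self report of drug use and stress and craving scales, will be assessed during the follow-up appointment". Under Drug and Alcohol Use Measures, the day-by-day Substance Use Calendar is collected "for the 60 days prior to treatment, weekly during treatment, and at the 30 day follow-up interviews".

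Section V.12 defines the first primary outcome as "Heavy drinking days (5 or more for men, 4 or more for women) during the 12 week period" and the second as any drinking days. Their main source is daily smartphone or telephone reporting, which Section X.2 (Payments) ties to the outpatient phase. Data Analytic Procedures plans intent-to-treat mixed models over weeks 1-2 and 3-12. It controls for gender, inpatient status and a three-level dropout variable: completer, out before 4 weeks, out after 4 weeks.

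**The concern.** Stopping at discharge is an offered route with its own payment totals, so it differs from ordinary loss to follow-up. Follow-up for this route is counted from the end of the inpatient phase, while the primary outcome runs to week 12. The end of the window therefore goes unmeasured by design.

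The decision comes after 3 to 4 weeks of blinded prazosin or placebo. Side effects, craving or perceived benefit could influence it, so the share who stop may differ by arm. The lost weeks lie after discharge, when drinking is possible, whereas the retained days include ward time, when it is largely prevented. The arm with more stoppers could look better with no drug effect, and days that were never measured cannot be recovered at analysis.

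**Working it through.** **1. How many follow-ups does an inpatient-only subject have?** Section X.2 gives totals of $450 with laboratory sessions and $235 without.

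- With: interview 25 + training 25 + three sessions 300 + bonus 50 + one follow-up 50 = $450.
- Without: three intake visits 60 + three ward weeks 75 + bonus 50 + one follow-up 50 = $235.

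Both totals reproduce with exactly one follow-up and no payment for daily reporting.

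**2. When is it?** The window is 12 × 7 = 84 days, taken to start with medication on the ward, because the model counts titration as weeks 1-2. Let W be ward days: 21 or 28. The text gives no taper length specific to stopping at discharge, so I use the plan's two taper texts: 5 days in Section V.3 and 7 days in Section VI.A.3.

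| W | Taper before the 30 days | Interview day | Week | Unmeasured days | Ward share of observed days |
|---|---|---|---|---|---|
| 21 | 0 | 51 | 7.3 | 33 (39%) | 21/51 = 41% |
| 28 | 0 | 58 | 8.3 | 26 (31%) | 28/58 = 48% |
| 21 | 5 | 56 | 8.0 | 28 (33%) | 21/56 = 38% |
| 21 | 7 | 58 | 8.3 | 26 (31%) | 21/58 = 36% |
| 28 | 5 | 63 | 9.0 | 21 (25%) | 28/63 = 44% |
| 28 | 7 | 65 | 9.3 | 19 (23%) | 28/65 = 43% |

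The last column assumes that the calendar at the interview reaches back to discharge and feeds the primary analysis. If it does not feed the analysis, ward days are 100% of observed days, and 84 − 28 = 56 to 84 − 21 = 63 days are missing.

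**3. What could this do to mean DD%?** Let p be the share of post-discharge days with drinking, equal in both arms (no drug effect), with no drinking on the ward and no taper added. Neither p nor the arm difference in stopping is in the documents; both are assumed.

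- True DD% = p × (84 − W)/84. At p = 30%: 0.30 × 63/84 = 22.5% (W = 21), or 0.30 × 56/84 = 20.0% (W = 28).
- Recorded with the calendar = 30p/(W + 30): 9/51 = 17.6%, or 9/58 = 15.5%.
- Recorded without it: 0%.
- Understatement per stopper: 4.9 or 4.5 points with the calendar; 22.5 or 20.0 without.
- Shift for a 10-point arm difference in stopping = 0.10 × understatement: 0.45 to 0.49 points with the calendar; 2.0 to 2.25 without.
- For p from 20% to 40%: about 0.3 to 0.65 with the calendar; 1.3 to 3.0 without.

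**4. How much of the trial is affected?** The share who stop is not stated. If 10% to 50% of all subjects did, lost person-days would run from 0.10 × 26/84 = 3% to 0.50 × 33/84 = 20% with the calendar, and from 0.10 × 56/84 = 7% to 0.50 × 63/84 = 38% without it.

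**The case against.** A reader might infer that these subjects' 12-week outcome rests mostly on ward days. The documents do not support that. The daily calendar is scheduled at the 30-day interview, so with it ward days are 36% to 48% of observed days. In the weeks 3-12 period, without the taper, they are only 7/37 = 19% to 14/44 = 32%. The stronger reading needs the calendar to be ignored, and nothing in the plan says that it will be.

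A reader might also take 2.0 to 2.3 points as the expected bias. That figure has the same worst-case premise and concerns raw means. The planned mixed models use each subject's available data over time and adjust for inpatient status and dropout, so neither shift is the bias of the planned estimator. The models still do not remove bias when stopping depends on unobserved drinking, and the plan states no missing-data assumption or sensitivity analysis.

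Finally, these subjects may be meant for the laboratory aims only. Section VII.11 lists a separate inpatient consent, so some may have chosen the route before any drug. Section V.12 labels the primary outcomes as belonging to the outpatient phase and sizes the clinical trial at 120, against 150 enrolled. This stands as an ambiguity, but it does not close the gap. The plan without laboratory sessions offers the same exit with its own payment total, and those subjects add nothing to the laboratory aim. No text removes either group from the intent-to-treat analysis.

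**Conclusion.** The gap is real. For an inpatient-only subject, 26 to 33 of 84 days are unmeasured, or 19 to 28 if the 30-day clock starts after the taper. The plan does not say whether such subjects enter the intent-to-treat analysis, whether their 30-day calendar is used, or which dropout code they receive.

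The likely effect on the drinking comparison is modest if the calendar is used (about 0.3 to 0.65 points of raw mean DD% under the assumptions above) and larger if it is not. It depends on a stopping share and an arm difference that the documents do not give. It would go too far to say that the 12-week intent-to-treat outcome does not exist for these subjects: it is partly observed, and its use is unspecified. The change is worth making because it is cheap and because analysis cannot restore the missing weeks.

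**What to change.** In the Follow-up paragraph and the Substance Use Calendar text of Section V.3, anchor the drinking follow-up of every randomised subject to week 12 from randomisation, whatever phase was completed or whenever medication stopped.

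- For inpatient-only subjects, hold the existing paid interview at week 12, by telephone if needed; Section V.3 supports telephone administration of the calendar.
- Have the calendar cover discharge to week 12. That is 56 to 63 days, close to the 60-day recall already used at baseline.
- Apply the same anchoring to outpatients who taper after the laboratory sessions.
- In Data Analytic Procedures, state that these data enter the intent-to-treat HDD% and DD% analyses, and which dropout code these subjects receive.

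The cost is protocol wording and one interview moved later. The downsides are longer recall (up to 3 days beyond the baseline precedent), a slightly higher risk of losing the subject before the interview, and a later date for these subjects' 30-day post-treatment measures, such as the ASI.

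This changes measurement only. No treatment or taper rule is proposed, but the 5-day and 7-day taper texts in Sections V.3 and VI.A.3 must be reconciled.
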